Uveitis and iritis have been associated with dabrafenib, while RPED and RVO have been associated with trametinib therapy. Monitor patients for visual signs and symptoms (such as change in vision, photophobia, and eye pain) during therapy. Special attention should be given to retinal findings (e.g., retinal pigment epithelial detachment (RPED) or retinovascular abnormalities (i.e., branch or central retinal vein occlusions [RVO])).

The ophthalmology exam will include best corrected visual acuity, visual field examination, tonometry, slit lamp biomicroscopic examination of the anterior segment (with special attention to inflammation) and the posterior segment, and dilated indirect funduscopy with special attention to retinal abnormalities. Optical coherence tomography is strongly recommended at scheduled visits and if retinal abnormalities are suspected. Other types of ancillary testing including color fundus photography, and fluorescein angiography may also be indicated as determined by clinical exam.

Guidelines regarding event management and dose reduction for visual changes considered to be related to study treatment are provided in the table below.

Rev. Add13 **Table 10: Dabrafenib-Trametinib Treatment Modification for Visual Changes**

CTCAE Grade	Management Guideline	Action and Dose Modification
Grade 1*	
 Consult ophthalmologist within 7 days of onset. 	
 If dilated fundus examination cannot be performed within 7 days of onset, hold trametinib until RPED and RVO can be excluded by retina specialist/ ophthalmologist. Dabrafenib may be continued. If RPED and RVO excluded, continue (or restart) trametinib at same dose level If Uveitis/Iritis, refer to table below for Iritis/Uveitis If RPED suspected or diagnosed, refer to RPED dose modification table below; report as SAE if diagnosed. If RVO diagnosed: Permanently discontinue trametinib and report as SAE according to the instructions in Section 5.2.
Grade 2 and Grade 3	
 Consult ophthalmologist immediately. 	
 Hold trametinib. Dabrafenib may be continued. If RPED and RVO excluded, restart trametinib at same dose level If Uveitis/Iritis, refer to table below for Uveitis/Iritis If RPED diagnosed, see RPED dose modification table below; report as SAE according to the instructions in Section 5.2 If RVO diagnosed: Permanently discontinue trametinib and report as SAE according to the instructions in Section 5.2.

CTCAE Grade	Management Guideline	Action and Dose Modification
Grade 4	
 Consult ophthalmologist immediately. 	
 Interrupt trametinib. Dabrafenib may be continued. If RPED and RVO excluded, may consider restarting trametinib at same or reduced dose after discussion with study PI. If Uveitis/Iritis, refer to table below If RVO or RPED diagnosed, permanently discontinue trametinib and report as SAE according to the instructions in Section 5.2.

Abbreviations: RPED = retinal pigment epithelial detachments; RVO = retinal vein occlusion; SAE = serious adverse event
 
* If visual changes are clearly unrelated to study treatment (e.g., allergic conjunctivitis), monitor closely but ophthalmic examination is not required.
		

Table 11: Dose Modification for RPED

Event CTCAE Grade	Action and Dose Modification
Grade 1 RPED (Asymptomatic; clinical or diagnostic observations only)	
 Continue trametinib with retinal evaluation monthly until resolution. If RPED worsens, follow instructions below. Dabrafenib treatment is not affected
Grade 2-3 RPED (Symptomatic with mild to moderate decrease in visual acuity; limiting instrumental ADL)	
 Interrupt trametinib. Continue dabrafenib Retinal evaluation monthly. If improved to \leq Grade 1, restart trametinib with one dose level reduction (reduced by 0.5 mg) or discontinue in patients taking trametinib 1 mg daily. If no recovery within 4 weeks permanently discontinue trametinib

Table 12: Dabrafenib-Trametinib Dose Modification for Uveitis and Iritis

CTCAE Grade	Action and Dose Modification
Uveitis and Iritis	
 Continue study treatment Control ocular inflammation with local therapies If not improved to grade ≤ 1 within 1 week, interrupt dabrafenib until resolution of ocular inflammation and then restart dabrafenib reduced by one dose level If no recovery within 4 weeks, permanently discontinue dabrafenib. Trametinib may be continued. For patients on Arm C consider that uveitis could be an IRAE from prior ipilimumab + nivolumab and treat accordingly

Dabrafenib-Trametinib Dose Modification for Pneumonitis

Pneumonitis has been observed in patients receiving trametinib in combination with dabrafenib. To reduce the risk of pneumonitis, patients will be monitored closely for symptoms, evaluated with imaging and functional tests when appropriate. For patients on Arm C, it should be considered that the pneumonitis could be an IRAE from

prior ipilimumab + nivolumab therapy and treated with corticosteroids as indicated until IRAE excluded.

Table 13: Dabrafenib-Trametinib Treatment Modification for Pneumonitis

CTCAE Grade	Adverse Event Management	Action and Dose Modification
Grade 1	
 CT scan (high-resolution with lung windows) recommended. Clinical evaluation and laboratory work-up for infection Monitoring of oxygenation via pulse-oximetry recommended Consultation with pulmonologist recommended 	
 Continue study therapy at current dose
Grade 2	
 CT scan (high-resolution with lung windows) recommended. Clinical evaluation and laboratory work-up for infection Consult pulmonologist Pulmonary function tests – if < normal, repeat every 8 weeks until ≥ normal Bronchoscopy with biopsy and/or BAL recommended Symptomatic therapy including corticosteroids if clinically indicated 	
 Interrupt trametinib until recovery to grade ≤ 1 Restart trametinib reduced by one dose level Escalation to previous dose level after 4 weeks may be considered after consultation with PI If no recovery to grade ≤ 1 within 4 weeks, permanently discontinue trametinib.
Grade 3	
 Same as grade 2 	
 Interrupt trametinib until recovery to grade ≤ 1 Resumption of trametinib at one dose level reduction may be considered after consultation with PI If no recovery to grade ≤ 1 within 4 weeks, permanently discontinue trametinib.
Grade 4	
 Same as grade 2 	
 Permanently discontinue trametinib.

Dabrafenib-Trametinib Dose Modification for Liver Chemistry Changes

For patients on Arm C, it should be considered that the liver chemistry changes could be in part an IRAE from prior ipi/nivo therapy and treated with corticosteroids as indicated until IRAE excluded.

Rev. Add13

Table 14: Dabrafenib-Trametinib Dose Modification for Liver Chemistry Changes

Event	Treatment modifications and assessment/monitoring

 ALT \geq 3x ULN but $<$ 5x ULN and TB $<$ 2x ULN, without symptoms considered related to liver injury or hypersensitivity and who can be monitored weekly for 4 weeks 	
 May continue study treatment. Report as SAE if CTEP-AERS reporting criteria is met. Report as SAE according to the instructions in Section 5.2 if CTEP-AERS reporting criteria is met. 
MONITORING: Repeat LFT (ALT, AST, ALK, bilirubin) until they return to normal/baseline or stabilize (LFT may be every 2 weeks after 4 weeks if ALT $<$ 3x ULN and TB $<$ 2 ULN).


Criteria for discontinuing study drug: When any of the liver stopping criteria below is met, discontinue trametinib and dabrafenib
 
 ALT \geq 3xULN and bilirubin \geq 2x ULN or $>$35% direct bilirubin ALT \geq 3xULN and INR $>$ 1.5, if INR measured (INR threshold does not apply if subject is on anticoagulant) ALT \geq 5x ULN ALT \geq 3x ULN persists for \geq 4 weeks ALT \geq 3x ULN and cannot be monitored weekly for 4 weeks ALT \geq 3x ULN associated with symptoms (new or worsening) believed to be related to liver injury or hypersensitivity 	
 Immediately discontinue study treatment. Report as SAE according to the instructions in Section 5.2 if: 1) CTEP-AERS reporting criteria are met, or 2) patients meet criteria 1-2. Perform liver event ASSESSMENT AND WORKUP (see below). Monitor the subject until liver chemistries resolve, stabilize, or return to baseline (see MONITORING below). If applicable, provide details on required follow up assessments (e.g., follow up for overall survival or disease recurrence or progression). [Do not include for single-dose studies] 
MONITORING: In patients stopping for criteria 1-2 (with abnormal TB and INR, indicating potentially more significant liver toxicities):
 
 Repeat liver chemistries (ALT, AST, ALK, bilirubin) and perform liver event follow-up assessments within 24 hours. Monitor subjects twice weekly until LFT return to normal/baseline or stabilize. A specialist or hepatology consultation is recommended. 
In patients stopping for criteria 2-6:
 
 Repeat LFT and perform liver event follow up assessments within 24-72 hours Monitor subjects weekly until LFTs return to normal/baseline or stabilize. 
ASSESSMENT and WORKUP:
 
 Viral hepatitis serology. Serum CPK and LDH. Fractionate bilirubin, if total bilirubin \geq 2x ULN. CBC with differential to assess eosinophilia. Record clinical symptoms of liver injury, or hypersensitivity on AE CRF. Record concomitant medications (including acetaminophen, herbal remedies, other over the counter medications). Record alcohol use. 
Additional work up for patient stopping for criteria 1-2 (with abnormal TB and INR, indicating potentially more significant liver toxicities):

Event	Treatment modifications and assessment/monitoring
	
 • Anti-nuclear antibody, anti-smooth muscle antibody, Type 1 anti-liver kidney microsomal antibodies, and quantitative total immunoglobulin G (IgG or gamma globulins). • Serum acetaminophen adduct HPLC assay (in subjects with likely acetaminophen use in the preceding). • If there is underlying chronic hepatitis B (e.g. positive hepatitis B surface antigen): quantitative hepatitis B DNA and hepatitis delta antibody. • Liver imaging (ultrasound, MRI, CT) and /or liver biopsy.

Dabrafenib-Trametinib Dose Modification for Venous Thromboembolism (VTE)

Event	Dabrafenib	Trametinib (When Used in Combination)
Uncomplicated DVT or PE	Do not modify the dose.	Withhold trametinib for up to 3 weeks. 
 • If improved to Grade 0-1, resume at a lower dose level. • If not improved, permanently discontinue.
Life Threatening PE	Permanently discontinue dabrafenib	Permanently discontinue trametinib.

Rev. 12/15, 6/16
Rev. 11/16, 2/17
Rev. Add14

5.4.2

Dose Modifications for Ipilimumab/Nivolumab

The treatment of events for ipilimumab and nivolumab alone, or in combination follow the same guidelines and algorithms. Patients experiencing grade 3 toxicities that require holding of therapy during the ipilimumab/nivolumab induction period (first 12 weeks) that resolve to grade 1 or less (off of > than physiologic replacement doses of corticosteroids) by week 16 may resume nivolumab monotherapy at the next scheduled maintenance dose according to protocol. Exceptions to this are: pneumonitis, nephritis and neurologic toxicities. Patients with toxicities that require dose holding, and/or steroid administration, but allow for continuation on therapy (e.g grade 2 rash) should omit the held dose (whether during induction or maintenance) and resume treatment with the next scheduled dose according to the original calendar. (Exception- If during induction period symptoms resolve to baseline within 7 days in the absence of immunosuppressive treatment patients may resume with omitted dose and postpone subsequent induction therapy by 1 week. Scans should still be done at Week 12 and first maintenance nivo dose should be omitted in order to get patient back on schedule). Patients who require omission of 2 consecutive doses of induction therapy should withhold further induction treatment and resume treatment with maintenance nivolumab monotherapy at the time of a scheduled dose (e.g. C3D1, C3D15 or C3D29 following resolution of toxicity).

Below are dose delay tables for nivolumab + ipilimumab for the following adverse events. Please refer to [Appendix X](#) in the protocol for toxicity management algorithms which include specific treatment

guidelines. These algorithms should be followed unless there are specific clinical circumstances which the treating physician indicates variations or alternative treatment is needed.

In several places there are differences regarding protocol directed drug modification rules identified with (^). In these cases please follow the protocol specific guidelines in this section.

Generally we strongly encourage early evaluation, withholding drug, and appropriate treatment as indicated in the management tables and following event specific guidelines.

NOTE: In the text that if a patient experiences several adverse events and there are conflicting recommendations, the investigator should use the recommended dose adjustment that reduces the dose to the lowest level.

NOTE: In the event that the dosing management outlined in Section 5.4.2 conflicts with [Appendix X](#) Management Algorithms, the EA6134 recommendation is to follow the Section 5.4.2 management guidelines.

ALL OTHER EVENTS*	Management/Next Dose for Nivolumab + Ipilimumab
≤ Grade 1	No change in dose
Grade 2	Hold until ≤ Grade 1 OR baseline. Resume at same dose level. For lab abnormalities, no change in therapy or dose.
Grade 3	Hold* until ≤ Grade 1 continue at investigator discretion
Grade 4	Off protocol therapy. For lab abnormalities, may restart at investigator discretion.
* non-immunologically mediated	
Recommended management: As clinically indicated	
ALL OTHER EVENTS**	Management/Next Dose for Nivolumab + Ipilimumab
≤ Grade 1	No change in dose
Grade 2	Hold until ≤ Grade 1 OR baseline. When resolved to ≤ Grade 1 and off of steroids for at least 1 week, resume at same dose level.
Grade 3	Off protocol induction therapy. May resume nivolumab monotherapy if resolved to Grade 1 or less (off of > than physiologic replacement doses of corticosteroids) by end of week 16. (exceptions noted in 5.4.2) If occurs with nivolumab monotherapy, then off protocol therapy.
Grade 4	Off protocol therapy
** immunologically mediated	
Recommended management: As clinically indicated	

Rev. Add14

Skin Rash and Oral Lesions	Management/Next Dose for Nivolumab + Ipilimumab
≤ Grade 1	No change in dose *
Grade 2	Hold/ omit therapy* until ≤ Grade 1 or resolved [^] . Consider oral steroid treatment if > 7 days. Resume at same dose level at time of an originally scheduled dose administration once toxicity returned to grade 1 and patient is off steroids.
Grade 3	Hold* until ≤ Grade 1. Resume at same level at investigator discretion
Grade 4	Off protocol therapy
* Patients with purpuric or bullous lesions must be evaluated for vasculitis, Steven-Johnson syndrome, TEN, and autoimmune bullous disease including oral lesions of bullous pemphigus/pemphagoid. Pruritus may occur with or without skin rash and should be treated symptomatically if there is no associated liver or GI toxicity. Note skin rash typically occurs early and may be followed by additional events particularly during steroids tapering.	
Recommended management: AE management guidelines	

Rev. Add14

Liver Function AST	Management/Next Dose for Nivolumab + Ipilimumab
≤ Grade 1	Continue protocol therapy.
Grade 2	Hold/ omit therapy until WNL or baseline. Consider oral steroid treatment if > 7 days. Resume at same dose level at time of an originally scheduled dose administration once toxicity return to grade 1 and patient off steroids.
Grade 3	Discontinue protocol induction therapy. Initiate IV or PO steroids. May begin nivolumab monotherapy if returns to grade 1 off steroids or other immunosuppressive treatment by week 16 (no earlier than week 13); if not returned to grade 1 after week 16, discontinue nivolumab monotherapy. Hold maintenance therapy. Initiate IV or PO steroids. If not returned to grade 1 off steroids by 6 weeks from missed dose, then off protocol therapy.
Grade 4	Off protocol therapy. Initiate IV steroids.
Continued treatment of patients with active immune mediated hepatitis may exacerbates ongoing inflammation. Holding drug to evaluate LFT changes and early treatment are recommended. LFT changes may occur during steroid tapers from other events and may occur together with other GI events including cholecystitis/pancreatitis.	
Recommended management: see Hepatic AE management algorithm	

Rev. Add14

Diarrhea/ Colitis	Management/Next Dose for Nivolumab + Ipilimumab
≤ Grade 1	Hold until Grade 0 (if Grade 1) or baseline [^] . No change in dose
Grade 2	Hold/ omit until Grade 0 or baseline. Oral steroid treatment if > 7 days and hold further induction therapy. May begin nivo monotherapy at time of a previously scheduled dose if resolved to grade 0 (or baseline) off of steroids by week 16.

Rev. Add14

Diarrhea/ Colitis	Management/Next Dose for Nivolumab + Ipilimumab
Grade 3	Off protocol therapy; may begin nivo monotherapy if resolved to grade 0 (or baseline) by week 16. If occurs during nivo monotherapy then patient is off protocol therapy.
Grade 4	Off protocol therapy

See GI AE Algorithm for management of symptomatic colitis (Appendix X).
 
Patients with \leq Grade 2 toxicity resolving to Grade 0 or baseline within 7 days in the absence of oral steroids during induction may resume with omitted dose and have treatment scheduled postponed 1 week. Scans should still be done at week 12 and first maintenance dose of nivo should be omitted. If during maintenance, dose should just be omitted and treatment resumed with next dose.
 
Patients with grade 2 symptoms but normal colonoscopy and biopsies may be retreated after resolution.
 
Patients who require steroids should be taken off study induction treatment.
 
Please evaluate pituitary function prior to starting steroids if possible without compromising acute care.
 
Evaluation for all patients for additional causes includes C. diff, acute and self-limited infectious and foodborne illness, ischemic bowel, diverticulitis, and IBD.
 
Recommended management: see GI AE management Algorithm; Patients with grade 2 toxicity requiring steroid therapy should not resume induction therapy.
	

Pancreatitis Amylase/Lipase	Management/Next Dose for Nivolumab + Ipilimumab
\leq Grade 1	Continue protocol therapy if asymptomatic
Grade 2	Continue protocol therapy if asymptomatic
Grade 3	Continue protocol therapy if asymptomatic at investigator discretion
Grade 4	If asymptomatic, hold protocol therapy until $<$ grade 2, then resume at same dose level.

Patients with symptomatic or radiologic evidence of pancreatitis as well as DM and DKA should be off protocol therapy. Lipase elevation may occur during the period of steroid withdrawal and with other immune mediated events or associated with colitis, hepatitis, and patients who have asymptomatic lipase elevation typically have self-limited course and may be retreated.
 
For treatment management of symptomatic pancreatitis please follow the Hepatic Adverse Event Management Algorithm
	

Pneumonitis	Management/Next Dose for Nivolumab + Ipilimumab
\leq Grade 1	Hold/ omit dose pending evaluation and resolution to \leq Grade 0 or baseline including baseline pO ₂ . Resume no change in dose after pulmonary and/or ID consultation
Grade 2	Hold/ omit dose pending evaluation. Resume no change in dose after pulmonary and/or ID consultation if lymphocytic pneumonitis is excluded. Off protocol therapy if steroids are required. ^
Grade 3	Hold/ omit dose pending evaluation. Resume no change in dose after pulmonary and/or ID consultation only if lymphocytic pneumonitis is excluded. Otherwise, off protocol therapy

Pneumonitis	Management/Next Dose for Nivolumab + Ipilimumab
Grade 4	Off protocol therapy
Distinguishing inflammatory pneumonitis is often a diagnosis of exclusion for patients who do not respond to antibiotics and have no causal organism identified including influenza. Most patients with respiratory failure or hypoxia will be treated with steroids. Bronchoscopy may be required and analysis of lavage fluid for lymphocytic predominance may be helpful. Patients with new lung nodules should be evaluated for sarcoid like granuloma. If seasonal influenza vaccine is considered, killed vaccines should be recommended.	
Recommended management: See Pulmonary Adverse Event Management Algorithm	

Other GI N-V	Management/Next Dose for Nivolumab + Ipilimumab
≤ Grade 1	No change in dose.
Grade 2	Hold/ omit pending evaluation for gastritis duodenitis and other immune adverse events or other causes. Resume at same dose level after resolution to ≤ Grade 1.
Grade 3	Hold/ omit pending evaluation until ≤ Grade 1. Resume at same dose level. If symptoms do not resolve within 7 days with symptomatic treatment patients should go off protocol induction therapy. May resume nivo monotherapy if resolved to grade ≤ 1 (off of > replacement steroids for 2 wks by wk 16)
Grade 4	Off protocol therapy
Patients with grade 2 or 3 N-V should be evaluated for upper GI inflammation and other immune related events.	

Fatigue	Management/Next Dose for Nivolumab + Ipilimumab
≤ Grade 1	No change in dose.
Grade 2	No change in dose
Grade 3	Hold/ omit until ≤ Grade 2. Resume at same dose level
Grade 4	Off protocol therapy
Fatigue is the most common adverse event associated with immune checkpoint therapy. Grade 2 or greater fatigue should be evaluated for associated or underlying organ involvement including pituitary, thyroid, and hepatic, or muscle (CPK) inflammation	

Rev. Add13

Neurologic events	Management/Next Dose for Nivolumab + Ipilimumab
≤ Grade 1	Hold dose pending evaluation and observation.^ If symptoms don't progress and processing below excluded may resume with no change in dose.*
Grade 2	Hold dose pending evaluation and observation.^ Hold until ≤ Grade 1. *Off protocol therapy if treatment with steroids is required.^ Resume at same dose level for peripheral isolated n. VII (Bell's palsy)^
Grade 3	Off protocol therapy

Neurologic events	Management/Next Dose for Nivolumab + Ipilimumab
Grade 4	Off protocol therapy
* Patients with any CNS events including aseptic meningitis, encephalitis, symptomatic hypophysitis, or myopathy, peripheral demyelinating neuropathy, cranial neuropathy (other than peripheral n. VII), GB syndrome, myasthenia gravis, should be permanently off IO treatment, but can remain on study. If the patient has disease progression and the toxicity from the IO has resolved, they should be able to cross over to targeted therapy.	
Recommended management: See Neurologic Adverse Event Management Algorithm	

Endocrine Hypophysitis Adrenal Insufficiency	Management/Next Dose for Nivolumab + Ipilimumab
≤ Grade 1	Asymptomatic TSH elevation. Add hormone replacement as clinically indicated. Continue therapy.
Grade 2	Hold/ omit until patients are on a stable replacement hormone regimen. Resume at same dose level.
Grade 3	Hold/ omit until patients are on a stable replacement hormone regimen. Resume at same dose level. If diagnosed with hypophysitis should hold induction therapy, but may begin nivo monotherapy when returned to grade 1 (must be no earlier than week 13 and by end of week 16)
Grade 4	Off protocol therapy

Note all patients with symptomatic pituitary enlargement, exclusive of hormone deficiency, but including severe headache or enlarged pituitary on MRI should be considered grade 3 events. Isolated thyroid or testosterone deficiency may be treated as grade 2 if there are no other associated deficiencies and adrenal function is monitored. Please evaluate pituitary function before beginning steroid therapy or replacement therapy of any kind.
 
 Note patients with thyroiditis may be retreated on replacement therapy. Patients must be evaluated to rule out pituitary disease prior to initiating thyroid replacement. Patients with symptomatic hyperthyroidism can be given a short course of a beta blocker (e.g propranolol). Hyperthyroidism usually converts to hypothyroid within 4 weeks. 	
Recommended management: See Endocrine Management Algorithm	

Fever	Management/Next Dose for Nivolumab + Ipilimumab
≤ Grade 1	Continue protocol therapy.
Grade 2	Hold/ omit until ≤ Grade 1. Resume at same dose level.
Grade 3	Hold/ omit until ≤ Grade 1. Resume at same dose level.
Grade 4	Off treatment
Patients with fever should be evaluated as clinically appropriate. Patients may experience isolated fever during infusion reactions or up to several days after infusion. Evaluation over the course of 1-2 weeks should be done for other autoimmune events that may present as fever	

Fever	Management/Next Dose for Nivolumab + Ipilimumab
See Section 5 . infusion reactions	

Cardiac*	Management/Next Dose for BMS-936558 (Nivolumab) + Ipilimumab Cardiac Toxicities
≤ Grade 1	Hold dose pending evaluation and observation.** Evaluate for signs and symptoms of CHF, ischemia, arrhythmia or myositis. Obtain history EKG, CK (for concomitant myositis), CK-MB. Repeat troponin, CK and EKG 2-3 days. If troponin and labs normalize may resume therapy. If labs worsen or symptoms develop then treat as below. Hold pending evaluation
Grade ≥ 2 with suspected myocarditis	Hold dose.** Admit to hospital. Cardiology consult. Rule out MI and other causes of cardiac disease. Cardiac Monitoring. Cardiac Echo. Consider cardiac MRI and cardiac biopsy. Initiate high dose methylprednisolone. If no improvement within 24 hours, add either infliximab, ATG or tacrolimus. Resume therapy at a time of next scheduled dose if there is a return to baseline and myocarditis is excluded or considered unlikely.
Grade ≥ 2 with confirmed myocarditis	Off protocol therapy. Admit to CCU (Consider transfer to nearest Cardiac Transplant Unit). Treat as above. Consider high dose methylprednisolone; Add ATG or tacrolimus if no improvement. Off treatment.

* Including CHF, LV systolic dysfunction, Myocarditis, CPK, and troponin
 
** Patients with evidence of myositis without myocarditis may be treated according as "other event"
 
NOTE: The optimal treatment regimen for immune mediated myocarditis has not been established. Since this toxicity has caused patient deaths, an aggressive approach is recommended.
	

 • Drug will be held for grade 2 cardiac dysfunction pending evaluation • Drug will be permanently discontinued for grade 3 or 4 cardiac dysfunction and grade 2 events that do not recover to baseline or that reoccur • Treatment with steroids as clinically indicated 	

Patients requiring a delay of > 6 weeks, or > 8 weeks for patients on high dose steroids with required 4 weeks minimum taper and 2 week observation, should go off protocol therapy, except as specified in Section [5.4.2](#) (Dose Modifications for Ipilimumab/Nivolumab).

Patients requiring > two dose delays/ dose omissions for the same event should go off protocol therapy.

Prior to starting corticosteroids or hormone replacement for any reason, appropriate endocrine testing including cortisol, ACTH, TSH and T4 must be obtained to document baseline.

Patients may be dose-delayed for evaluation and restarted depending on results.

Any patient started on corticosteroids initially who is determined to not require steroids treatment for an autoimmune adverse event may resume therapy after a 2 week observation period without further symptoms at the discretion of the PI or investigator. Therapy should

be resumed at the time of a next scheduled dose and held doses should be omitted or skipped.

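### Table 14 puts stopping criterion 2 on two post-stop monitoring schedules, and its continue-treatment row does not exclude patients who already meet a stopping criterion

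*Combined protocol and SAP*

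**What the plan says.** All of this is in Section 5.4.1, Table 14, unless stated.

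- **Row 1 (continue).** The patient has ALT at least 3x but below 5x ULN and total bilirubin (TB) below 2x ULN, "without symptoms considered related to liver injury or hypersensitivity and who can be monitored weekly for 4 weeks". The action is "May continue study treatment". The row sets no limit on the direct fraction or on INR.
- **Row 2 (stop).** "When any of the liver stopping criteria below is met, discontinue trametinib and dabrafenib". Six criteria follow. Criterion 1 joins ALT at least 3x ULN, bilirubin at least 2x ULN and more than "35% direct bilirubin" with an unbracketed and/or. Criterion 2 is ALT at least 3x ULN with INR above 1.5, if INR was measured and the patient is not anticoagulated.
- **Monitoring after stopping.** Criteria 1-2 are described as "with abnormal TB and INR, indicating potentially more significant liver toxicities". Liver chemistries are repeated within 24 hours, and then: "Monitor subjects twice weekly until LFT return to normal/baseline or stabilize". The next block opens "In patients stopping for criteria 2-6". It repeats tests within 24-72 hours, and then: "Monitor subjects weekly until LFTs return to normal/baseline or stabilize".
- **Other groupings.** The SAE-reporting line and the additional work-up line in the same row both treat criteria 1-2 as the serious pair.
- **Section 5.2.8** uses the wording of criteria 1 and 2 as triggers for a 24-hour expedited report in Arms B and C.

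**The concern.** These are operative safety rules, so a site should be able to read one action from the table for a given set of laboratory values. In two places it cannot do so directly. A patient who stops for criterion 2 is given two recheck schedules. And a patient can satisfy every condition for continuing while also satisfying a criterion that stops both drugs. What is at stake is consistent discontinuation and follow-up of hepatotoxicity across sites in Arms B and C.

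**Working it through.** No power or alpha figure is involved, so the check sets the rules side by side.

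**1. Post-stop schedule.**

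| Stopping criterion | Block headed 1-2 | Block headed 2-6 |
|---|---|---|
| 1 | yes | no |
| 2 | yes | yes |
| 3 to 6 | no | yes |

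Only criterion 2 is in both. Because the reporting and work-up lines group criteria 1 and 2, the second heading was evidently meant to start at 3.

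**2. Row 1 against each stopping criterion at one visit.** Row 1 fixes ALT (3x to below 5x ULN), TB (below 2x ULN), no symptoms and weekly monitoring possible.

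| Criterion | Can it hold together with row 1? |
|---|---|
| 1, through direct fraction above 35% | yes |
| 2, if INR is measured and above 1.5 | yes |
| 3, ALT at least 5x ULN | no, row 1 caps ALT |
| 4, ALT at least 3x ULN for 4 weeks or more | only later, as a time limit |
| 5, weekly monitoring not possible | no |
| 6, symptoms | no |

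So 2 of 6 criteria can coincide with row 1 at the same visit.

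**3. Does the answer depend on how the and/or in criterion 1 is bracketed?** The grid was ALT 2.9, 3, 4, 4.9, 5 x ULN; TB 0.4, 1, 1.9, 2, 3 x ULN; direct fraction 20, 35, 36, 50%. Row 1 admits 3 ALT values, 3 TB values and 4 direct fractions: 3 x 3 x 4 = 36 points. Of these, 3 x 3 x 2 = 18 have a direct fraction above 35%.

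| Reading of criterion 1 | Overlap with row 1 |
|---|---|
| ALT and (TB or direct) | 18 of 36 |
| (ALT and TB) or direct | 18 of 36 |
| ALT and TB, with direct above 35% | 0 of 36 |

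Both bracketings of the printed text overlap with row 1. The third reading does not, but it is not what is printed. The grid values are arbitrary, so 18 of 36 tests logic and is not a frequency.

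**4. What was intended?** The monitoring block describes criteria 1-2 as cases with abnormal TB, and the work-up asks for fractionation only when TB is at least 2x ULN. Both suggest that the direct fraction was meant to qualify a raised TB. As printed, it can bite at a low total: direct 0.2 of total 0.5 mg/dL is 0.2/0.5 = 40%.

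**5. Can it arise?** Direct and total bilirubin are both in the scheduled chemistry panel (Section 7.1.1, footnote 5), so the direct fraction will be seen. INR is not in that panel, so the criterion 2 overlap needs an INR taken for another reason. At entry, ALT up to 5x ULN is allowed only with documented liver metastases (3.1.14.6). TB up to 1.5x ULN is allowed with no cap on the direct fraction (3.1.14.8). Crossover to Arm C applies the same limits (3.2.1), but 3.2.4 also requires Step 1 toxicities to have resolved to grade 1 or less. Entry with raised ALT is therefore mainly a matter of liver metastases.

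**The case against.** The strongest reply is that a permission and a mandate do not truly conflict. A site that stops breaches nothing in row 1; a site that continues breaches row 2. Only stopping satisfies both. Section 5.4 also directs questions about how doses should be modified to the Study Chair, and on the printed wording the 24-hour report in 5.2.8 is owed whichever row a site follows. The two monitoring schedules can likewise be met together: a repeat within 24 hours also meets the looser window, and twice weekly covers weekly.

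Most of this stands, and it limits the point to inconsistent handling. It does not remove the point. Section 5.4.1 has no sentence ranking the rows; the nearby tie-break notes are in 5.4.2, for ipilimumab/nivolumab. The table's own clues on the direct fraction (step 4) give a careful site a reason to continue where another stops. And the permission-against-mandate argument does nothing for the duplicated criterion 2, where both schedules are instructions.

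A reader might also infer that a direct fraction above 35% stops treatment even with normal ALT. The punctuation allows that, but all six criteria open with an ALT threshold, so the reading is strained and is not relied on here.

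**Conclusion.** Table 14 has two internal inconsistencies: criterion 2 is assigned to two post-stop schedules, and row 1 does not exclude patients who meet criterion 1 through the direct fraction or criterion 2 through INR. Both follow from the printed text and hold under either bracketing of criterion 1. This is a minor safety-table correction.

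Three larger inferences are not supported. The documents give no frequency for these laboratory patterns, so no number of affected patients can be stated, and it could be zero. Twice weekly against weekly cannot be turned into a count of missed tests, because monitoring runs until recovery or stabilisation and no fixed period is set. Nothing here touches the 2-year OS comparison, its sample size or its error rate.

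The one open assumption is intent: whether the direct-bilirubin limb is meant to apply when TB is below 2x ULN. The table's wording suggests not, but only the medical team can settle it.

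**What to change.** 1. Change the second monitoring heading from criteria 2-6 to criteria 3-6.
2. Add to row 1: *and no stopping criterion below is met*. This is needed for criterion 2 whatever is decided about criterion 1.
3. Have the medical team decide first whether the direct-bilirubin limb applies when TB is below 2x ULN. Then write criterion 1 identically in Table 14 and 5.2.8, as one of:
   - *ALT >=3x ULN and TB >=2x ULN with direct >35%*; or
   - *ALT >=3x ULN and (TB >=2x ULN or direct >35%)*.

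The cost is one wording amendment to Table 14 and one bullet of 5.2.8, with no change to visits, scheduled tests or sample size. Each choice in item 3 has a consequence. Under the second, sites that would have continued under row 1 will stop both drugs for a direct fraction above 35% at TB below 2x ULN. Under the first, an asymptomatic patient with ALT 3x to below 5x ULN, TB at least 2x ULN and a direct fraction of 35% or less would fit neither row 1 (TB too high) nor criterion 1, so the amendment should also say how that patient is handled.
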